All personnel will be properly trained in the protocol and procedures expected of them. In addition, refresher training may be conducted, as needed. Training logs will be kept in the study regulatory binders.

Monitoring of the Study

The sites will perform self monitoring of this study.

Source Data

All source documents will be maintained in the research chart for each subject. In addition, electronic medical records (EMR) may also be utilized by the study facility. It is the practice of the research facility to allow EMR access to monitors or auditors, if requested.

Study Timetable and End of Study

Patient recruitment is expected to be completed within 2 years of initiating the study. Once the final patient has been recruited, follow-up will last for 2 additional years. The study duration is estimated at 4 years.

During the time of enrollment, patients will be seen every three months. This includes the 3 month visit, 6 month visit, 9 month visit, and 12 month visit. At the 12 month visit, patients will be given the opportunity to continue in the study for an additional 12 months. This would include the 15 month visit, 18 month visit, 21 month visit, and 24 month visit.

Data Management

All data will be recorded on preprinted case report forms (CRF) suitable for electronic data capture. The case report forms will be kept in the patient's research chart. The research charts will be stored in a locked, secure location. Data will be entered by qualified personnel at the conclusion of study.

Statistical Methods

Sample Size

This trial will be a pilot study. Outcome estimates will form the basis for assessing the feasibility of designing a future large and definitive trial. One hundred fifty patients in each study arm will be enrolled (300 total patients). Since each patient will receive 2 vein grafts, on average, there will be approximately 300 vein grafts in each group (600 vein grafts total). This sample size will be large enough to detect whether a clinically important difference exists in terms of vein graft patency between the groups, but small enough that subject recruitment can be performed in an expedient manner, likely within the first 24 months of the study.

This trial will not be designed or powered as a definitive clinical trial. Based on several previously published clinical trials, it is anticipated that 10-20% of vein grafts will be documented as occluded at the 1-year time point after CABG. Should ticagrelor improve graft patency and reduce vein occlusion from 20% to 10%, power calculations suggest that this pilot trial will have 96% power to detect a significant difference ($P<0.05$) between the groups. Alternatively, if ticagrelor were to decrease the occlusion rate from 15% to 10%, the power will be approximately 58%.

Statistical Analysis

All study data will be collected in a blinded fashion during the course of the trial. At 1- and 2-years after surgery, the CT coronary angiograms will be read and interpreted by board-certified radiologists with expertise in cardiac CT imaging. The radiologists will be blinded to study treatment assignment. The data analysis will also be performed in a blinded fashion, with un-blinding at the conclusion of the analysis. Study outcomes will be compared on an intention-to-treat basis according to the randomization study-group assignment. Vein graft occlusion, the primary outcome of the study, will be compared between the two randomization groups using a Fisher's exact test. To account for within-patient correlation and the possibility of multi-graft occlusion within individual patients, vein graft data will also be analyzed using logistic regression fit with generalized estimating equations methods. For secondary outcomes, continuous data will be compared between the two groups using two-sided Student's t tests, two-sample Wilcoxon rank-sum tests, or ANOVA, and a Fisher's exact test will be used for categorical data. Time to major adverse cardiovascular event will be determined for the study groups using the Kaplan-Meier method, and groups will be compared with a log-rank test. In accordance with intention-to-treat analysis, clinical and safety data will be analyzed for all randomized patients in the study. This will include data collected

from subjects who have dropped out of the trial or who refuse postoperative CT coronary angiography (5% expected refusal).

Study analysis will be performed at the 1-year and 2-year time-points. The first analysis will be conducted when the last recruited patient has passed the 1-year time interval after surgery and has undergone CT angiography. The second analysis will be performed when all recruited patients have crossed the 2-year time-point after surgery.

Important Medical Procedures to be followed by the Investigator

Overdose

If an overdose on an AstraZeneca study drug occurs in the course of the study, then the investigators or other site personnel will inform appropriate AstraZeneca representatives within one day (i.e. immediately but no later than the end of the next business day) of when he or she becomes aware of it.

The designated AstraZeneca representative will work with the Investigator to ensure that all relevant information is provided to the AstraZeneca Patient Safety data entry site.

Pregnancy

Patients who are pregnant or seeking to become pregnant will be excluded from trial recruitment. All outcomes of pregnancy, should they occur, will be reported to AstraZeneca.

References

1. American Heart Association: Heart Disease and Stroke Statistics - 2011 Update. Circulation. 2011;123:e1-e192.
5. Bourassa MG. Fate of venous grafts: the past, the present and the future. J Am Coll Cardiol. 1991;17:1081-3.
6. Fitzgibbon GM, Kafka HP, Leach AJ, Keon WJ, Hooper GD, Burton JR. Coronary bypass graft fate and patient outcome: angiographic follow-up of 5,065 grafts

related to survival and reoperation in 1,388 patients during 25 years. *J Am Coll Cardiol.* 1996;28:616-26.

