Overall, the experience with clopidogrel after CABG has been unimpressive in terms of improving graft patency or clinical outcomes. In keeping with the American Heart Association guidelines [40-41], the current standard of care for postoperative antiplatelet therapy is isolated aspirin therapy, in doses of 100-325 mg daily. Interestingly, a favorable experience with ticagrelor was recently noted after CABG. Like clopidogrel, ticagrelor inhibits the platelet P2Y₁₂ adenosine diphosphate receptor, but has a more rapid onset of action and more consistent and pronounced platelet inhibition than clopidogrel [42-43]. In the PLATO study, 18,624 patients with acute coronary syndrome were randomized for 1-year treatment with aspirin plus ticagrelor 90 mg twice daily or aspirin plus clopidogrel 75 mg daily. The primary end point of the study (cardiovascular death, MI, or stroke) was significantly reduced by ticagrelor compared to clopidogrel (9.8% versus 11.7%, ticagrelor versus clopidogrel, P<0.001) [42]. In a subsequent subgroup analysis of the 1,261 PLATO patients who underwent CABG, ticagrelor

treatment led to a non-significant reduction in the primary end-point at 1 year (10.6% versus 13.1%, ticagrelor versus clopidogrel, $P=0.29$), and a significant reduction in cardiovascular mortality (4.1% versus 7.9%, ticagrelor versus clopidogrel, $P<0.01$) [43].

To date, no data is available regarding the impact of ticagrelor on saphenous vein graft patency following CABG. Even with routine aspirin use after CABG, 10-20% of vein grafts occlude within 1 year after surgery, placing these patients at high risk for future myocardial events. In contrast to clopidogrel, ticagrelor treatment leads to a more pronounced platelet inhibition, and may substantially improve graft patency following CABG compared to aspirin therapy. We therefore propose a randomized controlled trial to compare postoperative graft patency between patients treated after CABG with aspirin therapy, the current standard of care, to those treated with ticagrelor starting in the early postoperative period.

Research Hypothesis

The hypothesis of this clinical trial is that ticagrelor treatment will improve postoperative saphenous vein graft patency 1 and 2 years after CABG surgery, as compared to standard aspirin therapy.

Study Rationale

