The primary objective of this clinical trial will be to evaluate whether, as compared to usual aspirin treatment, ticagrelor early after CABG prevents saphenous vein graft *occlusion* 1 year after surgery, as assessed by computed tomography (CT) coronary angiography, as well as 2 years after surgery via study extension.

Secondary Objective

The secondary objective of this clinical trial will be to evaluate whether, as compared to usual aspirin treatment, ticagrelor early after CABG prevents saphenous vein graft *stenosis*, defined as >50% narrowing of the graft, 1 year after surgery, as assessed by computed tomography (CT) coronary angiography, as well as 2 years after surgery via study extension.

Exploratory Objectives

Additional exploratory objectives of this clinical trial will include the impact of ticagrelor treatment, as compared to aspirin, on the incidence of major adverse cardiovascular events (mortality, myocardial infarction, cerebrovascular accident, hospitalization for coronary ischemia, and need for coronary intervention) and bleeding events in the first year and second year study after CABG (Appendix B). It is recognized that the study will be under-powered in the evaluation of these outcomes, which will be defined using the previously published definitions from the CURE and CASCADE trials [30, 39, 44]. Specifically, major bleeding episodes will be defined as substantially disabling bleeding, intraocular bleeding leading to the loss of vision, or bleeding necessitating the transfusion of at least 2 units of blood. Major bleeding is classified as life-threatening if the bleeding episode is fatal, leads to a reduction in the hemoglobin level of at least 5 grams per deciliter or to substantial hypotension requiring the use of intravenous inotropic agents, if it necessitates a surgical intervention, if it is a symptomatic intracranial hemorrhage, or if it necessitates the transfusion of four or more units of blood. Minor bleeding episodes will include other hemorrhages (i.e. nose bleeds) that lead to the interruption of the study medication.

Study Plan and Procedures

Overall Study Design

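### Vein graft occlusion is primary at both 1 and 2 years, but the plan gives no order, alpha rule, either/both rule or sidedness for the two analyses

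*Combined protocol and SAP*

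**What the plan says.** All references are to the combined protocol and SAP.

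- **Research Hypothesis:** "ticagrelor treatment will improve postoperative saphenous vein graft patency 1 and 2 years after CABG surgery", compared with aspirin.
- **Study Objectives, Primary Objective:** prevention of vein graft occlusion "1 year after surgery, as assessed by computed tomography (CT) coronary angiography, as well as 2 years after surgery via study extension". The Secondary Objective concerns a different outcome, stenosis, so 2-year occlusion is not placed below 1-year occlusion anywhere.
- **Statistical Methods, Sample Size:** the anticipated 10-20% occlusion rate is a 1-year rate. For 20% versus 10% the plan claims "96% power to detect a significant difference ($P<0.05$) between the groups", and for 15% versus 10% about 58%. This is the only place where a significance level is given.
- **Statistical Methods, Statistical Analysis:** "Vein graft occlusion, the primary outcome of the study, will be compared between the two randomization groups using a Fisher's exact test". No time point and no sidedness are attached. The same section says "Study analysis will be performed at the 1-year and 2-year time-points", and "The first analysis will be conducted when the last recruited patient has passed the 1-year time interval after surgery" and has had CT angiography.
- **Overall Study Design:** patients are invited to stay for the second year. Expected uptake is not given.

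**The concern.** Two analyses of the primary outcome carry the same standing, and nothing fixes in advance which of them settles the hypothesis. The first is due once the last patient has reached 1 year, before the 2-year data are complete. A non-significant 1-year result could therefore be followed by a primary claim at 2 years, and no text would rule it out. That second chance would rest on the patients who chose to enter the extension, which is the weaker data set. The error rate also depends on a success rule and a sidedness that the plan leaves open, so a reader cannot say what false-positive risk the trial runs.

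**Working it through.** **1. The plan's own power figures.** Inputs from Sample Size: about 300 grafts per arm; 20% v 10% and 15% v 10%. Power = Φ[(|pA − pB| − z·√(2p̄(1−p̄)/n)) / √((pA(1−pA) + pB(1−pB))/n)].

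- 20% v 10%: the standard errors are √(2×0.15×0.85/300) = 0.02915 and √((0.16+0.09)/300) = 0.02887. With z = 1.96: (0.1 − 0.05714)/0.02887 = 1.485, power 93.1%. With z = 1.645: (0.1 − 0.04796)/0.02887 = 1.803, power 96.4%.
- 15% v 10%: the standard errors are 0.02700 and 0.02693. With z = 1.96, power is 45.7%; with z = 1.645, 58.2%.

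The stated 96% and 58% fit one-sided 0.05, not two-sided 0.05. The plan does not say which was meant.

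**2. Correlation between the two tests.** The documents do not give it. I assume no treatment effect, occlusion p1 = 15% at 1 year and p2 = 20% at 2 years, occluded grafts staying occluded, and a share f of patients in the extension:

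ρ = √[p1(1−p2) / (p2(1−p1))] × √f = √(0.12/0.17) × √f = 0.840 × √f.

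This gives 0.84, 0.70 and 0.59 for f = 100%, 70% and 50%.

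**3. Error if 0.05 is used at each time point and either one suffices.** Bivariate normal:

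- any difference, two-sided: 1 − P(|Z1|<1.96, |Z2|<1.96)
- benefit only, two-sided tests: 1 − P(Z1<1.96, Z2<1.96)
- benefit, one-sided 0.05 tests: the same with 1.645

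| Extension uptake | Any difference, two-sided | Benefit only, two-sided | Benefit, one-sided 0.05 |
|---|---|---|---|
| 100% | 7.5% | 3.8% | 7.3% |
| 70% | 8.3% | 4.2% | 8.0% |
| 50% | 8.8% | 4.4% | 8.5% |

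The single-test values are 5%, 2.5% and 5%. With 1-year occlusion of 10-20%, a further 2-10 points by year 2 and uptake of 50-100%, the three columns become 6.6-9.2%, 3.3-4.6% and 6.4-8.9%.

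**4. The same question with the planned test.** I simulated two-sided Fisher tests with 150 patients per arm, two grafts each, and the occlusion rates of step 2 (40,000 trials per cell, standard error about 0.1-0.15 points). The entries are false differences in either direction at either time point.

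| Within-patient correlation (assumed) | Uptake 100% | 70% | 50% |
|---|---|---|---|
| 0 | 5.8% | 6.5% | 6.6% |
| 0.10 | 7.4% | 8.2% | 8.0% |
| 0.15 | 8.2% | 8.9% | 9.0% |
| 0.20 | 8.8% | 9.5% | 9.9% |

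Fisher's test is conservative for independent grafts: its two-sided size for a single look is about 3.6-4.0% at occlusion of 10-25%. Ignoring clustering pushes the other way, so part of the increase down this table comes from clustering rather than from the second look.

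**5. If benefit is required at both time points.** P(Z1<−1.96, Z2<−1.96) is 1.2%, 0.8% and 0.6% at the three uptakes, so there is no inflation. The probability of success then cannot exceed the 1-year power and will usually be lower, so the stated 96% and 58% would be upper limits only.

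**The case against.** The strongest case against has four parts.

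- **The hypothesis joins the time points with 'and'.** Read literally, both are required and no error is inflated. That reading is available, but no section states it as a rule, and the power statement does not match it.
- **The text leans towards 1 year.** One year comes first, year 2 is an extension by invitation, the power rests on a 1-year rate, and the first analysis uses complete 1-year data rather than an interim cut. This supports naming 1 year as primary. It does not show that the plan has already done so.
- **This is a pilot.** The Sample Size section says the trial is not designed or powered as definitive. That lowers the consequence. The same section, however, says the sample is large enough to detect a clinically important difference, and a significance test is planned.
- **The error rate is easy to overstate.** A reader might infer that the chance of falsely claiming a graft benefit is 7-9% instead of 5%. The documents do not support that as a plain statement. With two-sided tests, 7-9% counts false harm as well, and false benefit stays below 5% on the assumptions of step 3. The higher figure applies to benefit only if the tests are one-sided at 0.05; the power figures fit this, but the plan never says it.

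The last part stands in full and limits the conclusion. The others leave the gap open.

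**Conclusion.** The gap is real: one primary outcome, two time points, and no order, alpha rule, either/both rule or stated sidedness. Its numerical effect is conditional. It needs an either-time success rule and a 0.05 threshold at 2 years, both of which are inferred. Given those, the chance of a false difference in either direction is about 7.5-8.8% by normal approximation. With Fisher's test it is about 6-6.5% for independent grafts and about 8-9% at a within-patient correlation near 0.15. False benefit is about 3.8-4.4% against 2.5% with two-sided tests, or 7.3-8.5% against 5% with one-sided ones. All of this rests on assumed 2-year occlusion, permanence of occlusion and extension uptake. It would be wrong to conclude that the plan states a 5% trial-wide error rate and breaches it, because no such rate is stated. The pilot status makes this a correction the plan should have rather than a fatal flaw.

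**What to change.** Amend the Research Hypothesis, Primary Objective and Statistical Analysis sections to say that:

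1. Vein graft occlusion at 1 year is the single primary endpoint and alone decides the primary claim.
2. The primary test has a stated sidedness, and the power figures are restated to match. With two-sided 0.05 and 300 grafts per arm, the step 1 formula gives 93.1% and 45.7%, ignoring clustering.
3. Vein graft occlusion at 2 years is the first secondary endpoint, tested at 0.05 only if the 1-year test is significant. Otherwise it is reported as an estimate with a confidence interval.

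This should be settled before any unblinded 1-year result is available. The cost is wording. The 1-year test keeps its full alpha and no patients are added. By comparison, splitting alpha equally (two-sided 0.025 each) would give 1-year power of 88.5% and 34.8%. The downside of the fixed sequence is that a success at 2 years alone could not be claimed as primary.

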with guideline recommendations. A creatinine level will be obtained before the 1-year and 2-year CT coronary angiogram, given the potential renal toxic effects associated with intravenous contrast.

Trial Timeline

Rationale for Study Design and Doses

The TARGET study will be a randomized double-blind controlled trial, which will generate the highest quality data regarding the potential patency benefits associated with ticagrelor after CABG. The study design will ensure that ticagrelor patients do not receive aspirin, to prevent bleeding complications associated with dual antiplatelet therapy. For the control patients who receive aspirin, 81 mg bid (162 mg daily) will be used. This relates to the fact that post-CABG patients have relative aspirin resistance postoperatively, and 81 mg of aspirin daily may be insufficient as the sole antiplatelet therapy. This relative aspirin resistance of post-CABG patients constitutes yet another biologic basis for investigating of the use of ticagrelor after bypass surgery. A higher dose of aspirin (162 mg daily) will ensure that aspirin patients receive adequate antiplatelet treatment after CABG, in keeping with current clinical guidelines [41]. At 1- and 2-years after surgery, graft patency will be evaluated by CT coronary angiography. Compared to conventional coronary angiography, CT angiography is a non-invasive diagnostic test that does not require an arterial puncture or catheter manipulation within the aorta, native coronary arteries, or bypass grafts. In a meta-analysis of 14 studies, CT coronary angiography was shown to have a sensitivity of 97.6% and a specificity of 98.5% for the assessment of graft occlusion, as compared to conventional coronary angiography [45].

Subject Selection Criteria

Inclusion Criteria

For inclusion in the study, subjects should fulfill the following criteria:

1. Provision of informed consent prior to any study specific procedures
2. Female and/or male patients aged 18-90 years
3. Patients undergoing first-time CABG with at least 1 saphenous vein graft, irrespective of concurrent valve surgery

Exclusion Criteria

Subjects should not enter the study if any of the following exclusion criteria are fulfilled:

1. Inability to provide informed consent
2. Pregnancy or seeking pregnancy
3. Patients undergoing redo-CABG
4. Serum creatinine >1.8 mg/dL (need for contrast with CT coronary angiogram)
5. Hypersensitivity or allergy to aspirin or ticagrelor

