No data exist with BRILINTA regarding a hemostatic benefit of platelet transfusions.

Drug Discontinuation

In PLATO, the rate of study drug discontinuation attributed to adverse reactions was 7.4% for BRILINTA and 5.4% for clopidogrel. Bleeding caused permanent discontinuation of study drug in 2.3% of BRILINTA patients and 1.0% of clopidogrel patients. Dyspnea led to study drug discontinuation in 0.9% of BRILINTA and 0.1% of clopidogrel patients.

Common Adverse Events

A variety of non-hemorrhagic adverse events occurred in PLATO at rates of 3% or more. These are shown in Table 3. In the absence of a placebo control, whether these are drug related cannot be determined in most cases, except where they are more common on BRILINTA or clearly related to the drug's pharmacologic effect (dyspnea).

Table 3 Percentage of patients reporting non-hemorrhagic adverse events at least 3% or more in either group

	BRILINTA N=9235	Clopidogrel N=9186
Dyspnea ¹	13.8	7.8
Headache	6.5	5.8
Cough	4.9	4.6
Dizziness	4.5	3.9
Nausea	4.3	3.8
Atrial fibrillation	4.2	4.6
Hypertension	3.8	4.0
Non-cardiac chest pain	3.7	3.3
Diarrhea	3.7	3.3
Back pain	3.6	3.3
Hypotension	3.2	3.3
Fatigue	3.2	3.2
Chest pain	3.1	3.5

¹ Includes dyspnea, dyspnea exertional, dyspnea at rest, nocturnal dyspnea, dyspnea paroxysmal nocturnal

Bradycardia

In clinical studies BRILINTA has been shown to increase the occurrence of Holter-detected bradycardias (including ventricular pauses). PLATO excluded patients at increased risk of bradycardic events (e.g., patients who have sick sinus syndrome, 2nd or 3rd degree AV block, or bradycardic-related

syncope and not protected with a pacemaker). In PLATO, syncope, pre-syncope and loss of consciousness were reported by 1.7% and 1.5% of BRILINTA and clopidogrel patients, respectively.

In a Holter substudy of about 3000 patients in PLATO, more patients had ventricular pauses with BRILINTA (6.0%) than with clopidogrel (3.5%) in the acute phase; rates were 2.2% and 1.6% respectively after 1 month.

Gynecomastia

In PLATO, gynecomastia was reported by 0.23% of men on BRILINTA and 0.05% on clopidogrel.

Other sex-hormonal adverse reactions, including sex organ malignancies, did not differ between the two treatment groups in PLATO.

Lab abnormalities

Serum Uric Acid:

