10 OVERDOSAGE

There is currently no known treatment to reverse the effects of BRILINTA, and ticagrelor is not expected to be dialyzable. Treatment of overdose should follow local standard medical practice. Bleeding is the expected pharmacologic effect of overdosing. If bleeding occurs, appropriate supportive measures should be taken.

Other effects of overdose may include gastrointestinal effects (nausea, vomiting, diarrhea) or ventricular pauses. Monitor the ECG.

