14 CLINICAL STUDIES

The clinical evidence for the effectiveness of BRILINTA is derived from PLATO, a randomized double-blind study comparing BRILINTA (N=9333) to clopidogrel (N=9291), both given in combination with aspirin and other standard therapy, in patients with acute coronary syndromes (ACS). Patients were treated for at least 6 months and for up to 12 months. Study endpoints were obtained until the study was complete, even if drug was discontinued.

Patients who presented within 24 hours of onset of the most recent episode of chest pain or symptoms were randomized to receive BRILINTA or clopidogrel. Patients who had already been treated with clopidogrel could be enrolled and randomized to either study treatment. Patients could be included whether there was intent to manage the ACS medically or invasively, but patient randomization was not stratified by this intent. Subjects in the clopidogrel arm were treated with an initial loading dose of clopidogrel 300 mg, if previous clopidogrel therapy had not been given prior to

BRILINTA® (ticagrelor) Tablets

randomization. Patients undergoing PCI could receive an additional 300 mg of clopidogrel at investigator discretion. All subjects randomized to BRILINTA received a loading dose of 180 mg followed by a maintenance dose of 90 mg twice daily. Concomitant aspirin was recommended at a loading dose of 160–500 mg. A daily maintenance dose of aspirin 75–100 mg was recommended, but higher maintenance doses of aspirin were allowed according to local judgment.

Because of ticagrelor's metabolism by CYP3A enzymes, the protocol recommended limiting the maximum dosage of simvastatin and lovastatin to 40 mg in both study arms. Because of an increased bleeding risk, the study excluded patients with previous intracranial hemorrhage, a gastrointestinal bleed within the past 6 months, or other factors that predispose to bleeding.

PLATO patients were predominantly male (72%) and Caucasian (92%). About 43% of patients were >65 years and 15% were >75 years.

The study's primary endpoint was the composite of first occurrence of cardiovascular death, non-fatal MI (excluding silent MI), or non-fatal stroke. The components were assessed as secondary endpoints.

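### Neither exclusion list has a bradycardia-risk criterion, so hemodynamically stable, unpaced patients with conduction disease can be randomized within days of surgery, about half of them to blinded ticagrelor

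*Combined protocol and SAP*

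**What the plan says.** The main list, under Subject Selection Criteria, Exclusion Criteria, begins "Subjects should not enter the study if any of the following exclusion criteria are fulfilled" and has 11 items. They cover consent, pregnancy, redo surgery, creatinine, drug hypersensitivity, anticoagulation, three bleeding criteria, severe hepatic impairment and strong CYP3A4 inhibitors. Appendix A repeats these and adds one item: low cardiac output needing more than two inotropes at 48 hours. Neither list has an item on heart rhythm or conduction.

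Overall Study Design has study drug starting on postoperative days 1 to 5, and Subject Enrollment and Randomization places randomization within 5 days of surgery. Treatment is double-blind, with 150 patients per arm.

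The label in Appendix C, under Bradycardia, says "BRILINTA has been shown to increase the occurrence of Holter-detected bradycardias (including ventricular pauses"). It then says "PLATO excluded patients at increased risk of bradycardic events", giving as examples sick sinus syndrome, second- or third-degree AV block and syncope due to bradycardia, where no pacemaker protects the patient. It also reports these PLATO results:

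- Ventricular pauses early on: "more patients had ventricular pauses with BRILINTA (6.0%) than with clopidogrel (3.5%) in the acute phase".
- Ventricular pauses later: "rates were 2.2% and 1.6% respectively after 1 month".
- Symptomatic events: "syncope, pre-syncope and loss of consciousness were reported by 1.7% and 1.5% of BRILINTA and clopidogrel patients, respectively".

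Section 14 of the label states: "The clinical evidence for the effectiveness of BRILINTA is derived from PLATO".

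**The concern.** The protocol's own appendix describes a rhythm effect of the study drug. It also reports that the trial supplying the efficacy evidence kept out the patients most exposed to that effect. TARGET would admit them, gives no reason for doing so, and offers no safety data for them.

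The timing adds to the concern. Drug starts in the first days after heart surgery, and the excess of pauses in PLATO was clearest early. Because treatment is blinded, a clinician who sees new bradycardia does not know whether ticagrelor is involved. What is at stake is the safety of a small group of participants. The primary graft analysis is not affected.

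**Working it through.** The plan states no figure on this point, so there is none to reproduce. The main check is a comparison of texts, and the arithmetic only gives scale.

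**Step 1: the two lists against the PLATO exclusion.** None of the 11 items in the main list, nor the twelfth in Appendix A, refers to sick sinus syndrome, AV block, syncope from bradycardia or pacemaker status. The inclusion criteria are broad: age 18-90 and first-time CABG with at least one vein graft, with or without valve surgery. They do not close the gap.

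**Step 2: other limits on randomization.** Overall Study Design and Restrictions during the Study add limits on hemodynamic support and anticoagulation only. Subject Enrollment and Randomization requires clinical stability, but explains it by hemodynamic support and risk of perioperative death. A stable patient with sick sinus syndrome or second-degree block would pass.

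**Step 3: size of the reported drug effect.** The inputs are the rates in Appendix C. The label gives about 3000 Holter patients; I assume 1500 per arm, all assessed at both times.

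- Acute phase: 6.0 - 3.5 = 2.5 points. SE = sqrt(0.06×0.94/1500 + 0.035×0.965/1500) = 0.775 points. 95% CI = 2.5 ± 1.96×0.775 = 1.0 to 4.0.
- After 1 month: 2.2 - 1.6 = 0.6 points. SE = sqrt(0.022×0.978/1500 + 0.016×0.984/1500) = 0.498 points. 95% CI = -0.4 to 1.6.
- With only 1250 per arm, the intervals are 0.84 to 4.16 and -0.47 to 1.67, which read the same way.
- Syncope-type events: 1.7 - 1.5 = 0.2 points.

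These rates support an early drug effect. They do not give the risk in the patients at issue, because PLATO had excluded those patients. PLATO also used a 180 mg loading dose (label section 14) that TARGET's regimen does not list, and its control was clopidogrel, not aspirin.

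**Step 4: scale and recruitment cost.** The documents give no prevalence of unpaced conduction disease, so p is assumed. Randomized = 300p. On ticagrelor = 150p. Otherwise eligible patients needed to randomize 300 = 300/(1-p). Added months, at a constant pace over the planned 24 = 24×(1/(1-p) - 1).

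| Assumed p | Randomized | On ticagrelor | Needed for 300 | Added months |
|---|---|---|---|---|
| 1% | 3 | 1.5 | 303.0 | 0.24 |
| 2% | 6 | 3 | 306.1 | 0.49 |
| 4% | 12 | 6 | 312.5 | 1.00 |

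**The case against.** The strongest defense is that the protocol follows the label. It carries over all four contraindications in label section 4 and the advice against strong CYP3A inhibitors. Bradycardia risk is not in section 4 and has no heading among the warnings in the label's contents. The instruction nearest to this point is in the overdosage section: "Other effects of overdose may include gastrointestinal effects (nausea, vomiting, diarrhea) or ventricular pauses. Monitor the ECG". That says nothing about eligibility at the normal dose. This stands, and it rules out calling the omission a label breach.

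Second, PLATO's criteria do not bind another trial, and TARGET already departs from them. PLATO excluded a gastrointestinal bleed within 6 months, while TARGET excludes any such history. True, but that departure is in the cautious direction. It also shows that TARGET's list goes beyond the label's contraindications where the sponsor saw a risk.

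Third, the evidence of clinical harm is thin. The pauses were Holter findings, the symptomatic difference was 0.2 points, and the one-month interval includes zero. This also stands. It cannot reassure about the patients PLATO left out, however.

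Fourth, existing provisions give some protection. The stability requirement probably holds back the most unstable cases, such as unpaced third-degree block, and an investigator is consulted on eligibility. Unblinding, withdrawal from drug, and stopping for attributable serious events are also available. These narrow the gap to hemodynamically stable patients. They do not close it, since they are discretionary or act after an event, and none is specific to rhythm.

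**Conclusion.** The omission is a fact of the text. Hemodynamically stable, unpaced patients with these conditions are eligible for randomization, and about half would receive blinded ticagrelor. The case for change rests on three things: a drug effect described in the protocol's own appendix, a precedent exclusion in the same place, and a very low cost. It merits an optional improvement and nothing stronger.

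Neither the number affected nor the harm can be estimated from the documents. The 3-12 randomized patients, about 1.5-6 of them on ticagrelor, follow from an assumed 1-4% and equal allocation.

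A reader might infer more, and the documents do not support it:

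- That the plan violates the label. It does not, because the label reports the PLATO exclusion without making it a contraindication or a recommendation.
- That every such patient would start ticagrelor. They are eligible for randomization, with an even chance of each arm.
- That harm in this group has been shown. There are no data on this group in either direction.
- That rhythm goes unmonitored. The Trial Timeline content and a figure are not reproduced in the text available, so nothing can be concluded about monitoring.

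**What to change.** Add one line to the main exclusion list and to Appendix A:

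*Sick sinus syndrome, 2nd or 3rd degree AV block, or bradycardia-related syncope, not protected by a permanent pacemaker, judged at randomization from the clinical record. Temporary postoperative pacing does not count as protection. A patient whose block has resolved by randomization (within 5 days of surgery) remains eligible.*

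The statements on temporary pacing and resolved block are needed because the criterion is applied days after heart surgery, with concurrent valve procedures allowed. Appendix A already has one criterion judged after surgery (the inotrope item), so the line fits beside it. If the sponsor wants to keep these patients in, a sentence giving the reason would serve instead.

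The cost is one line in two places. No new test or visit is needed, provided the clinical record already holds the rhythm information; the documents do not establish this, so the sites should confirm it. A few patients become ineligible and generalizability narrows slightly. Recruitment would take about 0.2 month longer at an assumed 1% and about 1 month longer at 4%.
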